6. GENERAL ANALYSIS DEFINITIONS

6.1 TREATMENT(S)

There will be 5 treatment study phases in this trial: screening, placebo run-in, study treatment phase (with either 10 mg Empagliflozin or matching placebo), post-treatment and post-study. The purpose of the definitions below is to describe all the different study/treatment intervals, in which a patient can lie during the course of the trial.

Table 6.1: 1 Treatment regimens / study intervals

Label	Interval	Start date	Start time
Screening	Screening	Date of informed consent	00: 00
Run-in	Run-in	Date of first administration of run-in medication	Time of first administration of run-in medication 12:00 if missing
Placebo/Emp agliflozin 10mg	Treatment	Date of first administration of trial medication	Time of first administration of trial medication 12:00 if missing
Post-treatment	Post-treatment	Date of last intake of trial medication + 1 day	00:00
Post-study	Post-study	Last contact date + 1 day	00:00

For efficacy and safety analyses, measurements will still be considered on-treatment during a follow-up period specific to each parameter. These follow-up periods are defined in [Table 6.7: 1.](#)

The efficacy analyses will follow the intention-to-treat (ITT) principle in assigning patients to treatment groups, i.e. patients will be analysed as randomised.

Safety analyses will be run on the treated set (TS). Patients will be shown under the randomised treatment. Safety analyses will also assign patients to the treatment group as randomised. In the exceptional case that a patient took the wrong treatment, adverse events may occur while being on the wrong treatment. Analyses of this data are described in [Section 7.8.1.7.](#)

6.2 IMPORTANT PROTOCOL DEVIATIONS

A protocol deviation (PD) is important, if it affects the rights or safety of the study patients, or if it can potentially influence the primary outcome measurement in a non-negligible way [\(4\)](#).

The documentation of the iPd categories, definition and how to handle iPdS in the analysis are done in the DV domain and stored within the TMF in EDMS.

6.3 SUBJECT SETS ANALYSED

The following analysis sets will be defined for this trial.

SCR - Screened patients set

All patients screened for the trial, with informed consent given and who completed at least one screening procedure at Visit 1.

RS - Randomised set

All patients from the screened set who were randomised to trial medication, regardless of whether any trial medication was taken.

TS – Treated set

All patients randomized and treated with at least one dose of trial medication. The TS is the basis for safety analyses.

FAS - Full analysis set

All patients randomised, treated with at least one dose of trial medication, and with a baseline and at least one on-treatment HbA1c value. The FAS is the basis for the ITT analysis.

PPS - Per-protocol set

All patients in the FAS without iPD leading to exclusion.

In [Table 6.3: 1](#) the data sets which are to be used for each category class of endpoint are illustrated. Note that the number of patients with available data for an endpoint may differ. For details, see [Section 6.6](#) “Handling of missing data and outliers”.

Table 6.3: 1 Summary of which data sets will be used for which class of endpoints

Class of endpoint	TS	FAS	PPS
Primary endpoint		OC, OC-IR, LOCF	OC
Subgroup analyses of primary endpoint		OC	
Further endpoints (binary)		NCF	
Further endpoints (continuous)		OC, OR#	
Safety endpoints	OR, OC-IR [^]		

#OR results will only be presented for time to first rescue medication and number of patients with rescue.

[^]OC-IR will be used for secondary endpoints and laboratory measurements.

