7.5 DETERMINATION OF SAMPLE SIZE

Based upon previous experiences with these compounds, the difference in HbA1c change from baseline after 52 weeks between the treatment groups can be assumed to be 0.5% with a standard deviation of 0.85%. With a randomisation ratio of 1:1, it is assumed that the sample size of each group (empagliflozin 10 mg and placebo) is 62 patients. Assuming that approximately 3% of patients will not be eligible for inclusion into FAS due to the absence of a post-baseline primary endpoint value, 64 patients for the empagliflozin 10 mg group and 64 patients for the placebo group need to be randomised. With this sample size, a power of 90% for a two-sided test at level $\alpha=5\%$ for the primary endpoint will be achieved.

Calculations were performed using nQuery Advisor® 6.1 statistical package by [REDACTED]
[REDACTED].

8. INFORMED CONSENT, TRIAL RECORDS, DATA PROTECTION, PUBLICATION POLICY, AND ADMINISTRATIVE STRUCTURE

The trial will be carried out in compliance with the protocol, the ethical principles laid down in the Declaration of Helsinki, in accordance with the ICH Harmonised Guideline for GCP, relevant BI Standard Operating Procedures (SOPs), the Japanese GCP regulations (Ministry of Health and Welfare Ordinance No. 28, March 27, 1997), Good Post-Marketing Study Practice (GPSP), Good Vigilance Practice (GVP) and other relevant regulations. Investigators and site staff must adhere to these principles. Deviation from the protocol, the principles of ICH GCP or applicable regulations will be treated as “protocol deviation”.

Standard medical care (prophylactic, diagnostic and therapeutic procedures) remains the responsibility of the treating physician of the patient.

The investigator will inform the sponsor immediately of any urgent safety measures taken to protect the trial patients against any immediate hazard, as well as of any serious breaches of the protocol, of ICH GCP, or of Japanese GCP.

The Boehringer Ingelheim transparency and publication policy can be found on the following web page: trials.boehringer-ingelheim.com. The rights of the investigator and of the sponsor with regard to publication of the results of this trial are described in the investigator contract. As a rule, no trial results should be published prior to finalisation of the clinical trial report.

The certificate of insurance cover is made available to the investigator and the patients, and is stored in the ISF.

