6.6.2.5 Non-completers considered failure (NCF)

For binary endpoints, like a treat to target response of HbA1c < 7.0%, a method that missing values are replaced as “failures” will be considered. Missing data due to early discontinuation per the completer definition will be replaced as “failure” (i.e., HbA1c $\geq 7.0\%$) up to the

planned final visit to be reached by all patients. In addition, values obtained after rescue medication will also be handled as “failure”.

For binary endpoints that are derived from quantitative endpoints (e.g. HbA1c), missing values within a course of measurements on treatment will be replaced on the basis of the corresponding imputed value of the underlying quantitative endpoint (e.g. interpolation for HbA1c).

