6.7 BASELINE, TIME WINDOWS AND CALCULATED VISITS

With regard to efficacy and safety endpoints, the term “baseline” refers to the last observed measurement prior to administration of any randomised trial medication. Measurements taken prior to the first intake of randomised trial medication will be considered pre-treatment values. Since the protocol specifies that all measurements are taken at Visit 3 before any intake of trial medication, all measurements at the first day of drug intake are assumed to qualify as baseline assessments.

Measurements taken after the first intake of randomised trial medication will be considered on-treatment values if they have been obtained up to end of the parameter specific follow-up period as defined in [Table 6.7:1](#) below and will be assigned to the randomised trial medication for efficacy and safety analyses.

Measurements taken after the end of the endpoint specific follow-up period and after the last intake of trial medication will be considered post-treatment values.

On-treatment efficacy, safety, health related and QoL measurements will be assigned to visits based on time windows around the planned visit dates. These time windows are defined based on the planned number of days after the date of first administration of trial medication (see [Table 6.7: 2](#)).

Table 6.7: 1 Endpoint specific assignment to active treatment

Endpoint	Last day of assignment to treatment phase
-----------------	--

		(days after trial medication stop date)
Efficacy		
HbA1c		7
Safety		
Adverse events		7
Safety laboratory measurements		3
Pulse rate		1
FPG		1
Chair stand test		7
Grip strength		7
Body composition		7
[REDACTED]		[REDACTED]

Reasons to base the time windows on the actual treatment start date rather than the randomisation date are:

- If first intake of trial medication shows a large delay by e.g. more than one week after the date of randomisation, a measurement taken four weeks after randomisation rather reflects the drug effect after three weeks than after four weeks and thus may underestimate the treatment effect at this visit.
- With large delays of the introduction of trial medication after the randomisation, the time window for the first on-treatment visit could include times the patient was not yet on trial medication.

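### NCF responder analysis is run on the FAS, so treated patients who stop with no on-treatment HbA1c are left out instead of counted as failures

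*SAP*

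**What the plan says.** SAP 6.6.2.5 sets the rule for binary endpoints: "Missing data due to early discontinuation per the completer definition will be replaced as" failure, through to the last scheduled treatment visit. Values after rescue are failures too. An HbA1c target below 7.0% is given as an example.

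SAP Table 6.3: 1 has one NCF entry, for binary further endpoints, in the FAS column. The TS and PPS cells of that row are empty. SAP 6.3 defines the two relevant sets:

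- FAS: "All patients randomised, treated with at least one dose of trial medication, and with a baseline and at least one on-treatment HbA1c value".
- TS: "All patients randomized and treated with at least one dose of trial medication", with no condition on HbA1c.

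Table 6.7: 1 treats HbA1c as on-treatment up to 7 days after the last dose. Beyond that, SAP 6.7 says: "Measurements taken after the end of the endpoint specific follow-up period and after the last intake of trial medication will be considered post-treatment values". A later HbA1c therefore does not bring a patient into the FAS.

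The protocol expects some patients to fall outside the FAS. Section 7.5 plans the sample size "Assuming that approximately 3% of patients will not be eligible for inclusion into FAS due to the absence of a post-baseline primary endpoint value", randomising 64 per arm to obtain 62.

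**The concern.** A failure under NCF is established by the fact of stopping early. It needs no post-baseline HbA1c. The FAS condition serves an analysis of change from baseline, which cannot use a patient without a post-baseline value. Applied to a rule with its own failure imputation, it removes patients whose outcome the rule has already settled.

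Two treated patients who stop early are thus handled differently. One with an HbA1c inside the 7-day window counts as a failure. One without it leaves both numerator and denominator. A table labelled as counting non-completers as failures would omit some of them, and each omission raises the response rate reported for that arm.

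**Working it through.** **1. The plan's own figures.** Protocol 7.5 gives a difference of 0.5, SD 0.85, two-sided alpha 0.05 and 90% power. By the normal approximation, n per arm = 2 × (1.960 + 1.282)² × (0.85/0.5)² = 2 × 10.51 × 2.89 = 60.7, so 61. The t-test needs 62 (power 0.901 at 62 and 0.897 at 61). Allowing for 3%, 62/0.97 = 63.9, so 64. The plan's 62 and 64 reproduce. The 3% is about 2 patients per arm, 4 of 128.

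**2. Who is left out.** HbA1c is drawn at every visit except Visit 2 (Protocol 5.1.1), and the first scheduled value after baseline is at Week 4. The Week 4 analysis window opens on Day 2 (SAP Table 6.7: 2). A patient who stops in week 2 is in the FAS if an HbA1c is taken within 7 days of the last dose. The same patient is outside it if the next sample is later than that or never taken.

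**3. Effect on one arm's rate.** A responder must have an on-treatment HbA1c, so all R responders are in the FAS. With m treated non-completers excluded from 64:

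- FAS rate = R/(64 − m)
- TS rate = R/64 = FAS rate × (64 − m)/64

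At m = 2 the FAS rate is too high by a factor of 64/62 = 1.032. The documents give no response rates, so a range is assumed.

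| Assumed FAS rate | TS rate, m = 2 | Overstatement, m = 2 | Overstatement, m = 4 |
|---|---|---|---|
| 10% | 9.7% | 0.3 points | 0.6 points |
| 20% | 19.4% | 0.6 | 1.3 |
| 30% | 29.1% | 0.9 | 1.9 |
| 40% | 38.8% | 1.3 | 2.5 |
| 50% | 48.4% | 1.6 | 3.1 |

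**4. Effect on the treatment difference.** Assume 24 of 64 responders on empagliflozin and 8 of 64 on placebo. The TS difference is 37.5% − 12.5% = 25.0 points. Let 4 patients in total be excluded.

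| Excluded (empagliflozin + placebo) | FAS rates | FAS difference | Shift |
|---|---|---|---|
| 4 + 0 | 24/60 = 40.0%, 8/64 = 12.5% | 27.5 | +2.5 |
| 3 + 1 | 24/61 = 39.3%, 8/63 = 12.7% | 26.6 | +1.6 |
| 2 + 2 | 24/62 = 38.7%, 8/62 = 12.9% | 25.8 | +0.8 |
| 1 + 3 | 24/63 = 38.1%, 8/61 = 13.1% | 25.0 | 0.0 |
| 0 + 4 | 24/64 = 37.5%, 8/60 = 13.3% | 24.2 | −0.8 |

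**5. Against sampling error.** On the same assumed rates the standard error of the difference is √(0.375 × 0.625/64 + 0.125 × 0.875/64) = 0.073, or 7.3 points. The balanced shift of 0.8 is about 0.1 standard errors. The extreme shift of 2.5 is about a third of one.

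**The case against.** The strongest reply is that the plan already catches most such patients. A note to SAP Table 6.7: 2 requires a Visit 8 after premature discontinuation. Protocol 6.2.2 places an end-of-treatment visit within 7 days of stopping for a patient who declines further follow-up. A reader might infer that all the earliest drop-outs disappear from the analysis. The documents do not support that: only those with no sample in the window are lost. This part of the reply stands and narrows the point. It does not close the gap, because the protocol itself expects about 3% outside the FAS.

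A reader might also infer a bias in favour of empagliflozin. That does not follow. Protocol 1.4 reports that adverse events leading to discontinuation were similar to placebo in completed studies, and Table 1.4.2: 1 expects more treatment failure on placebo. The split between arms is unknown, and the mirror cases above leave the difference unchanged or lower it.

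A third inference would be that the rescue endpoints should move to the TS as well, since a footnote to Table 6.3: 1 keeps them in the FAS row: "OR results will only be presented for time to first rescue medication and number of patients with rescue". That is not supported either. Protocol 3.3.4.1 and 6.2.2 allow new antidiabetic therapy after trial drug is stopped, and longer follow-up could count it as rescue. The endpoint's definition, in SAP 5.3.2, is not in the public text.

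Further endpoints are exploratory (Protocol 7.1), and SAP 7 already plans to report the number of patients in each analysis set by treatment group. Both points stand and lower the priority. The further-endpoint sections are also not public, so a supporting analysis on a wider set cannot be ruled out. The visible table names none.

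**Conclusion.** The mismatch is real and small. NCF as assigned in Table 6.3: 1 omits treated patients who stop without an HbA1c between first dose and 7 days after last dose, and SAP 6.6.2.5 would make them failures. Within an arm the direction is certain: each such patient removed raises the rate. At 2 per arm the excess is 0.3 to 1.6 points for assumed FAS rates of 10% to 50%. For the treatment difference neither the sign nor the size is known in advance. It ranges from −0.8 to +2.5 points on the assumed 24/64 and 8/64 with 4 exclusions.

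This rests on the protocol's 3%, on all 4 excluded patients having been treated (patients never treated would be outside the TS as well), and on response rates that are not in the documents. The primary MMRM does not depend on it.

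**What to change.** In SAP Table 6.3: 1, move the NCF entry for binary further endpoints from the FAS column to the TS column. Add to SAP 6.6.2.5 that a treated non-completer without an on-treatment HbA1c is a failure. Leave the rescue endpoints where they are.

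No new data are needed. The TS is already defined and already used for the secondary endpoints. A baseline HbA1c should exist for these patients, because a screening value is an entry criterion and baseline is the last value before the first randomised dose.

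The cost is one table entry, one sentence and one programming filter. Response rates will be slightly lower, and the responder tables will have a different denominator from the other efficacy tables, which needs a footnote. The change should also be checked against the further-endpoint sections that are not public.

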6.5 POOLING OF CENTRES

This section is not applicable, because centre is not included in the statistical model.

6.6 HANDLING OF MISSING DATA AND OUTLIERS

Based on the different reasons of patients' data missing for different endpoints, various methods will be used to assess the impact of missing data on the efficacy endpoints of this trial, depending upon the type of the endpoint (see [Table 6.3: 1](#)).

6.6.1 Definition of rescue therapy for censoring

For some of the imputation methods defined below, values after rescue medication will be set to missing. In this context, the following two situations are defined as use of rescue medication:

- Additional antidiabetic medication used for ≥ 7 consecutive days
- Increased in dose of background medication for ≥ 7 consecutive days

This approach will be used when considering which data to exclude from the OC and LOCF analyses. For this definition of rescue therapy no statistical analysis will be conducted. For the definition of rescue therapy as a further endpoint, please refer to [Section 5.3.2](#).

6.6.2 Imputation methods

6.6.2.1 Original result (OR) analysis

Original result analysis implies the analysis of data exactly as observed. OR analysis will be performed on endpoints that are either not affected by patients' rescue medication use or if it is not meaningful to apply any imputation rule on them for replacing the missing values.

6.6.2.2 Observed cases (OC) analysis

For all efficacy endpoints, it is planned to analyse only the available data that were observed while patients were on treatment, i.e., excluding the missing data. In other words, OC analysis will be performed and missing data in this analysis will not be replaced. Also, all values measured after rescue medication will be handled as missing (rescue medication as defined in [Section 6.6.1](#)).

The OC-technique represents the primary data selection tool that will be used for the primary analysis in this trial. Subsequent handling of missing data will be performed via a likelihood based method, and in the case of the primary analysis, will use the MMRM model.

6.6.2.3 Observed cases analysis including values on rescue medication (OC-IR)

For some endpoints the OC-technique will also be adapted without setting the values measured after rescue medication taken to missing, and using the original observed values instead. This is also done as a sensitivity analysis of the endpoint with OC as the imputation rule and will be called Observed Cases including values on rescue medication (OC-IR).

6.6.2.4 Last observation carried forward (LOCF)

An alternative method for quantitative endpoints is to replace missing values due to early discontinuation of a patient by her/his last observed measurement on treatment.

The last observation on-treatment need not necessarily be a value selected as a visit value if multiple measurements were performed within a time window for a visit. In this case the last on-treatment value within the time window will be carried forward, while the visit value can be the value that was observed closest to the planned visit date or the first value observed in the time window. See [Table 6.7: 2](#) for further details.

For example, if a patient is on rescue medication after Visit 3 and before Visit 4, then all the on-treatment visits will be set to missing and the HbA1c value from baseline will be carried forward to populate the missing on-treatment values in HbA1c.

Missing values within a course of measurements on treatment will be interpolated based on the last observed value before the missing visit and the first observed value after the missing visit. This is independent from the selection of a value as the picked visit value to be used in the descriptive analysis by visit.

The missing endpoint value can be interpolated as $E0 = E-1 + ((E1 - E-1) \times (D0 - D-1)) / (D1 - D-1)$, where

D0 = date of a visit with a missing endpoint value,

D1 = date of the next-visit (with end-point value non-missing) after the visit with missing endpoint,

D-1 = date of a previous-visit (with end-point value non-missing) before the visit with missing endpoint, and

Ei = endpoint values for visits D-1, D0 and D1 for i = -1, 0 and 1.

The values measured after rescue medication was taken during the active treatment period by the patients will be set to missing; and these missing values will be imputed by LOCF technique.

Missing data will only be imputed up to the planned visit to be reached by all randomised patients (Week 52).

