7.2.2 Primary endpoint analyses

For primary endpoint, refer to Section [2.1.2](#). The primary analysis will be performed on the FAS with treatment assignment as randomised.

The primary analysis is a restricted maximum likelihood (REML)-based mixed model repeated measures (MMRM) comparing the change in HbA1c (in units of %) from baseline after 52 weeks of double-blind treatment.

The statistical model will include fixed classification effects for treatment, gender, baseline renal function, visit and visit-by-treatment interaction, and a linear covariate for baseline HbA1c and age. An unstructured covariance structure will be used to model the within-patient errors. If this unstructured covariance structure fails to converge, the following structures will be tested: compound symmetry, variance components and Toeplitz. The covariance structure converging to the best fit, as determined by Akaike's information criterion, will be used.

The Kenward-Roger approximation will be used to estimate the denominator degrees of freedom.

Only the available data that were observed while patients were on treatment will be included in the analysis. Missing data are handled implicitly by the above statistical model, rather than using any imputation. This approach, referred to as observed case (OC), will additionally set all values measured after rescue medication taken to missing.

Sensitivity analyses of the primary endpoint will be performed. Such sensitivity analyses will be specified in the TSAP.

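### LOCF is a fixed single imputation, so its agreement with the primary MMRM would not show that the HbA1c result is robust to departures from missing at random

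*SAP*

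**What the plan says.** The primary analysis is an MMRM on the FAS, using on-treatment HbA1c with post-rescue values set to missing (Protocol 7.2.2; SAP 6.6.2.2 and 7.4.1). Protocol 7.2.2 states: "Missing data are handled implicitly by the above statistical model, rather than using any imputation". It defers sensitivity analyses of the primary endpoint to the SAP.

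For the primary endpoint, the visible SAP Table 6.3: 1 lists OC, OC-IR and LOCF on the FAS, and OC on the PPS. OC-IR (6.6.2.3) restores values measured after rescue.

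SAP 6.6.2.4 describes LOCF as a way to "replace missing values due to early discontinuation of a patient by her/his last observed measurement on treatment". Values after rescue are deleted and filled in by the same rule, up to Week 52. In the SAP's own example, a patient starts rescue after Visit 3 and before Visit 4, and "the HbA1c value from baseline will be carried forward to populate the missing on-treatment values in HbA1c".

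Under SAP 6.7, HbA1c taken more than 7 days after the last dose is post-treatment. Protocol 3.3.4.1 and 6.2.2 nevertheless provide for following discontinuers to the end of the trial and encouraging them to attend the remaining visits.

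**The concern.** The assumption most exposed in the primary analysis is that unobserved Week 52 values resemble those predicted from similar patients still on treatment and unrescued. A useful sensitivity analysis changes that assumption in a stated direction and shows how far the result moves.

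LOCF does not do this. It replaces one untested assumption with another, a flat course after the last on-treatment value, and then treats the filled-in value as if it had been measured. An empagliflozin patient who stops keeps the on-drug value to Week 52. A patient rescued before the first on-treatment HbA1c is given no change, although Protocol Table 1.4.2:1 itself expects treatment failure, with rising HbA1c, to be likelier on placebo.

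At stake is the supporting evidence, not the primary estimate. If LOCF and the MMRM agree, a reader could take the result as robust to missing data when that has not been examined. For discontinuers, LOCF is the only visible analysis that departs from the primary handling.

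**Working it through.** **1. The plan's own figure.** Protocol 7.5 gives a difference and SD that "can be assumed to be 0.5% with a standard deviation of 0.85"%, "a power of 90% for a two-sided test at level" 5%, and 1:1 allocation.

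- Normal approximation: n per arm = 2(z₀.₉₇₅ + z₀.₉₀)²σ²/δ² = 2 × (1.960 + 1.282)² × 0.85²/0.5² ≈ 60.7, so 61.
- Noncentral t: power is 0.8966 at 61 and 0.9014 at 62, so 62.
- Loss: 62/0.97 = 63.9, so 64 randomised per arm.

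The stated 62 and 64 reproduce. The 3% covers only patients with no post-baseline value. It is not a rate of rescue or later discontinuation, so every rate below is an assumption.

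**2. What each listed analysis does with the values at issue.**

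| Analysis | After discontinuation (beyond 7 days) | After rescue, on treatment |
|---|---|---|
| OC, FAS (primary) | not used; implicit MAR | set to missing; implicit MAR |
| OC-IR, FAS | not used; implicit MAR | observed values used |
| LOCF, FAS | last on-treatment value | last pre-rescue value (baseline if none) |
| OC, PPS | as primary, in a subset | as primary, in a subset |

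No row varies the unobserved post-discontinuation values.

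**3. Discontinuers, where the target effect includes loss of benefit off drug.** Assume a proportion p of empagliflozin patients stop, have the full 0.5-point effect at their last on-treatment value, and lose it by Week 52. LOCF overstatement = p × 0.5.

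- p = 5%: 0.025 (difference 0.475)
- p = 10%: 0.05 (difference 0.45)
- p = 20%: 0.10 (difference 0.40)

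**4. Early rescue, where the target is the no-rescue course.** Assume a proportion p of placebo patients are rescued before their first on-treatment HbA1c, remain in the FAS, and would otherwise have risen by c points. LOCF shrinks the difference by p × c.

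- 2% × 0.3 = 0.006
- 5% × 0.5 = 0.025
- 10% × 1.0 = 0.10

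Steps 3 and 4 use different target effects and must not be netted against each other.

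**5. Does LOCF agreement carry information about missing at random?** A simulation used 400 trials per scenario, 62 per arm and five visits. Maximum likelihood with unstructured covariance stood in for the MMRM. Drop-out depended on the last observed value, with about 13% missing at Week 52 on empagliflozin and 20-21% on placebo. The unobserved empagliflozin Week 52 values were then worsened by 0, 0.5 or 1.0 points. Rates, correlations and mean profiles are assumed; the Monte Carlo SE is about 0.008.

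| Mean profile | Worsening | True difference | MMRM | LOCF |
|---|---|---|---|---|
| Flat | 0 | -0.490 | -0.488 | -0.490 |
| Flat | 0.5 | -0.437 | -0.498 | -0.498 |
| Flat | 1.0 | -0.385 | -0.508 | -0.508 |
| Drifting | 0 | -0.500 | -0.502 | -0.499 |
| Drifting | 0.5 | -0.438 | -0.504 | -0.499 |
| Drifting | 1.0 | -0.365 | -0.490 | -0.487 |

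The two methods agree whether or not missing at random holds.

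**6. What a tipping point would report.** SE = 0.85 × √(2/62) = 0.1527. The smallest significant difference is t₀.₉₇₅,₁₂₂ × SE = 0.302. If 0.5 is observed and a proportion m of empagliflozin values is missing, significance is lost when those values are worse by (0.5 − 0.302)/m: 3.96, 1.98 or 0.99 points for m = 5%, 10% or 20%. This holds the SE fixed and ignores imputation variance. LOCF yields no comparable quantity.

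**The case against.** Several objections stand and limit the point.

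- **Few patients get zero change.** It applies only to rescue in about the first four weeks. Fasting glucose above 200 mg/dL in run-in is already an exclusion, double-blind rescue needs a confirmed value (Protocol 4.2.1), and SAP 6.6.1 requires at least 7 consecutive days of use. Later rescues carry the last pre-rescue HbA1c. A reader might infer that all rescued patients are scored as unchanged; the text does not say so.
- **Rescue is already addressed.** OC-IR uses the observed post-rescue values. The gap that remains is discontinuation.
- **The label is modest.** The SAP presents LOCF as an alternative and expressly calls only OC-IR a sensitivity analysis. Nothing says that LOCF tests missing at random or will be reported as robustness.
- **Redaction.** Parts of the SAP, including items in section 4, are blacked out or absent. A reader might conclude that no other sensitivity analysis exists. The visible table shows none, but that cannot be confirmed.
- **Different targets.** For an effect on drug without rescue, keeping a discontinuer's on-drug value is not in itself false benefit. Carrying forward an early value could also understate the effect; SAP 6.7 warns of underestimation at the first visit for slowly reacting parameters.
- **Arm imbalance is only partly documented.** The protocol expects more treatment failure on placebo, but section 1.4 reports AEs leading to discontinuation as similar to placebo.
- **The simulation result follows by construction.** Only unobserved values were worsened, so no method fitted to the observed data could respond. That is a limit of the demonstration, but it is also why an explicit departure has to be specified.

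The objection that the tipping values are large, two to eight times the planned effect, does not remove the need. It presumes an observed difference of 0.5 and low missingness, neither of which is yet known.

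**Conclusion.** The point holds in a limited form. LOCF as specified does not vary the unobserved HbA1c values, understates their uncertainty, and cannot show that the primary result withstands departures from missing at random. No analysis in the visible Table 6.3: 1 does so for values after discontinuation.

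The possible distortion in the LOCF estimate is modest at the assumed rates: 0.025-0.10 points upward for 5-20% of empagliflozin patients discontinuing, if the effect of interest includes loss of the 0.5-point benefit. Against a no-rescue target, early rescue of 2-10% of placebo patients with a rise of 0.3-1.0 points gives 0.006-0.10 points towards the null. The rates and rises are assumptions, and the net direction is unknown.

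It would be tempting to conclude that LOCF favours empagliflozin, or that the primary estimate is biased. The documents support neither: the two LOCF rules can pull in opposite directions, and the primary MMRM does not use LOCF.

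**What to change.** Before unblinding, add two analyses of the primary endpoint to SAP Table 6.3: 1 and section 6.6.2:

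- **(a)** control-based multiple imputation of Week 52 HbA1c after discontinuation or rescue, using the off-treatment HbA1c already collected where available;
- **(b)** a delta-adjusted tipping-point analysis that worsens the imputed empagliflozin values step by step until significance is lost.

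Combine both with Rubin's rules, and state the target effect of each. For (a), also state how off-treatment values are used once a new antidiabetic drug has been started, which Protocol 6.2.2 allows. Keep OC-IR. Keep LOCF only as a descriptive analysis, and say that its agreement with the MMRM is not evidence of robustness. If the redacted text already contains such analyses, list them in Table 6.3: 1.

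The cost is SAP wording and some programming, and a supportive estimate that may be less favourable. No new data are needed, and the primary analysis and sample size do not change.
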